**Version Number: v.8.1**

**Revision: 19 October 2023**

**Original: 28 April 2020**

## **Summary of Changes from Previous Version:**

Affected Section(s)	Summary of Revisions Made	Rationale
1.3, 8.1, 8.3.1	Added Charlson Comorbidity Index to SoA and correction to SoA, harmonization of 8.1 with 1.1 objectives, error found in 8.3.1	Charlson Comorbidity Index was requested by BACPAC other changes were corrected to text.
2.3.1, 6.3, 7.1, 8.2, 8.2.1, 9.4.7, 10.1.1.2,	

Stratified randomization by recruitment site.

Added method for flagging patients with severe depression and SUD symptoms

Revision showing AppliedVR server is HIPPA compliant

Addition of cannabinoids to comedications comprehensive list of measures for confidentiality added from MOP

Addition of mood disturbance and radicular pain added to sub-group analysis

A description of additional language added to consent is provided.

	These changes were made due to recommendations from the DSMB.

1.1, 1.3, 5.4, 5.5, 6.1.1, 6.2.4, 7.2, 8.2.1, 9.4.9,
	
 
Replacing Charge 3 for Charge 4
 
Additional surveys added to SoA
 
Revision to Screen Failure definition
 
Change in interval of review for the race/ethnicity data to monthly assessment
 
Updated definition of Skills-based VR intervention
 
Change in withdraw policy
 
	
These changes were made to provide the most up-to-date technology for the participants as well as update the feasibility of the protocol.


1.1, 1.3, 3.0, 8.2.1, 9.4.9, 8.1, 5.5
	
 
Addition of tertiary objective of interest sleep quality (seconds of light/deep sleep) from the Fitbit
 
An update was made to SoA showing increased frequency of Event assessment
 
Needed to remove the AppliedVR tablet for data collection as that will not be available.
 
Additional subgroups added to the subgroup analysis based on additional questions added to study
 
The plan for retention has been updated.
 
Information added for CURES application
 
A revision in patient compensation was made
 
	
Changes were made to harmonize with the SAP and up-to-date information from the virtual reality vendor. We wanted to add in info related to our CURES application. We also improved the compensation to provide compensation earlier in the study.

3, 7.3, 8.2, 8.2.1, 8.3.3.1, 10.1.1.2
	
 
Minor edits, updated language
 
AE assessment frequency “weekly” instead of “biweekly”.
 
	
Minor edits

5.5, 7.3, 8.2.1, 11
	
 
Loss to follow-up definition revised
 
Added info regarding AppliedVR VR usage data
 
Addition of Appendix: Diversity, Inclusion, & Equity Supplement
 
Updated 5.5 to reflect updated recruitment diversity benchmarks
 
	
Necessary changes to study operations, addition of supplemental funding initiatives as appendix

11.2
	
 
Recruitment objectives modified to incorporate treating physician letter
 
	
Protocol reflects procedures and new hybrid recruiting strategy

	
 
• Diversity supplement interview methodology updated to reflect that we did not record interviews and we drew from PAB waitlist
 
	
1, 8.2, 8.3.1	
 
• Depression alert procedures updated to include actions to take when telephone assessment cannot be made; approved by DSMB
 
• Neck pain and rash added as a known risk, borrowing approved language from STUDY00001363.
 
• Table of contents page numbers updated
 
	With DSMB guidance, created a contingency plan in the event that severely depressed individuals are lost to follow-up. List of known potential AEs updated to reflect oversight of known neck pain risk and to incorporate the incidence of allergy to face foam used in VR goggles.
5.5, 8.2, 10.1.1.2	
 
• Onboarding procedures modified to take into account new instructional videos
 
• Compliance procedures clarified and modified to account for optional SMS text messaging via REDCap
 
• Remove 7 day wait after emailing recruitment letter
 
• Removal of procedure for mailing study flyer
 
	Onboarding procedures now incorporate clear video instructions, and compliance monitoring updated to reflect current streamlined practices. General housekeeping on procedures to align with other VR trials.
7.2	
 
• Modified definition of replaceable participant to exclude individuals who used VR intervention before withdrawing from study
 
	Study adequately powered based on withdrawals to date, and analyses should include individuals who found the intervention unsatisfactory and subsequently withdrew
7.2, 12	
 
• Clarified confusing language in replaceable participant definition from previous mod
 
• Addition of Appendix B: Digital Divide Supplement
 
	Typos in language confused our new definition of a replaceable participant. Second sub-study added to appendix prior to initiation of new methods.
13	
 
• Addition of Appendix C: Cultural Barriers to VR Supplement
 
	Third sub-study added to appendix.

13.2, 13.3	
 
• Addition of post-interview quantitative “Interviewer Sentiment Scale” to Appendix C
 
• Disclose payment and requirement to complete both interview and questionnaire
 
	Directly capture effectiveness of AI interviewer
------------	--	--

*Abbreviations*

AE	Adverse Event
CFR	Code of Federal Regulations
clBP	Chronic Low Back Pain
CONSORT	Consolidated Standards of Reporting Trials
CBT	Cognitive Behavioral Therapy
CRF	Case Report Form
DSMB	Data and Safety Monitoring Board
eCRF	Electronic Case Report Forms
EHR	Electronic Health Record
GLP	Good Laboratory Practices
HIPAA	Health Insurance Portability and Accountability Act
IRB	Institutional Review Board
ITQ	Immersive Tendency Questionnaire
LBP	Lower Back Pain
MOOP	Manual of Operating Procedures
MRN	Medical Record Number
NCT	National Clinical Trial
NIH	National Institutes of Health
OHRP	Office for Human Research Protections
PI	Principal Investigator
QA	Quality Assurance
QC	Quality Control
SAE	Serious Adverse Event
SAP	Statistical Analysis Plan
SOA	Schedule of Activities
UP	Unanticipated Problem
US	United States
VR	Virtual Reality

## STATEMENT OF COMPLIANCE

The trial will be carried out in accordance with International Conference on Harmonisation Good Clinical Practice (ICH GCP) and the following:

- United States (US) Code of Federal Regulations (CFR) applicable to clinical studies (45 CFR Part 46, 21 CFR Part 50, 21 CFR Part 56, 21 CFR Part 312, and/or 21 CFR Part 812)

National Institutes of Health (NIH)-funded investigators and clinical trial site staff who are responsible for the conduct, management, or oversight of NIH-funded clinical trials have completed Human Subjects Protection and ICH GCP Training.

The protocol, informed consent form(s), recruitment materials, and all participant materials will be submitted to the Cedars-Sinai Institutional Review Board (IRB) for review and approval. Approval of both the protocol and the consent form must be obtained before any participant is enrolled. Any amendment to the protocol will require review and approval by the IRB before the changes are implemented to the study. In addition, all changes to the consent form will be IRB-approved; a determination will be made regarding whether a new consent needs to be obtained from participants who provided consent, using a previously approved consent form.

## 1 PROTOCOL SUMMARY

### 1.1 SYNOPSIS

**Title:** Randomized-controlled trial of virtual reality therapy for chronic low back pain to improve patient-reported outcomes and physical activity.

**Study Description:** This study will test the efficacy of an evidence-based virtual reality (VR) therapy program as a non-pharmacological supplement to management of chronic lower back pain. Study participants will be randomized to receive one of three VR programs: Skills-Based VR, Distraction VR, or Sham VR. In addition to a VR headset, all participants will receive a Fitbit Charge 4 watch. Study devices will be delivered to the participant's home with instructions for use via FedEx; participants will receive remote technical support. They will be followed for 90 days and complete Patient Reported Outcome (PRO) questionnaires to assess functional status, pain levels, and use of pain medications (including opioids). Participants will also be asked to provide consent/authorization to access medical records from their treating facility.

**Objectives:**

Primary Objective:

To assess the efficacy of immersive Skills-Based VR and Distraction VR in improving perceived pain from baseline to Day 30.

Secondary Objective:

To assess the efficacy of immersive Skills-Based VR and Distraction VR in improving perceived pain interference from baseline to Day 60 and Day 90.

To assess the efficacy of Skills-Based and Distraction VR in improving self-reported perceptions of sleep quality, sleep depth, and restoration associated with sleep from baseline to Day 90.

To assess the efficacy of Skills-Based and Distraction VR in improving self-reported perceptions of anxiety from baseline to Day 90.

To assess the efficacy of Skills-Based and Distraction VR in improving self-reported pain catastrophizing from baseline to Day 90.

To assess the efficacy of Skills-Based and Distraction VR in reducing use of opioids from baseline to Day 90.

Tertiary Objectives:

To assess the efficacy of Skills-Based and Distraction VR in improving self-reported physical function from baseline to Day 90.

To assess the efficacy of Skills-Based and Distraction VR in improving self-reported depression from baseline to Day 90.

To assess the efficacy of Skills-Based and Distraction VR via patients' global impression of change (PGIC).

To assess the efficacy of Skills-Based and Distraction VR in improving wearable measures of physical activity from baseline to Day 90.

To assess the efficacy of Skills-Based and Distraction VR in improving wearable measures of sleep quality from baseline to Day 90.

To assess the effect of presence on the efficacy of Skills-Based and Distraction VR in improving measures of pain interference from baseline to Day 30.

To assess the effect of Immersive Tendencies on the efficacy of Skills-Based and Distraction VR in improving measures of pain interference from baseline to Day 30.

To assess the effect of dose on the efficacy of Skills-Based and Distraction VR in improving measures of pain interference from baseline to Day 30.

**Endpoints:** Primary Endpoint: Change in PROMIS Pain Interference  
Secondary Endpoints: Change in PROMIS Sleep Disturbance, PROMIS Anxiety, Pain Catastrophizing, MME usage.

**Study Population:** Individuals ages 13 or older with an ongoing low back-pain problem that has persisted at least 3 months and has resulted in pain on at least half the days in the past 6 months.

**Phase:** Phase 2

[figure not shown]
**Description of Sites/Facilities Enrolling Participants:** Three outpatient clinic sites, including the Cedars-Sinai Orthopaedic Clinic, Cedars-Sinai Medical Network Chronic Pain Program, and Attune Health, a musculoskeletal clinic affiliated with Cedars-Sinai. In addition, participants may enroll remotely.

**Description of Study Intervention:** All participants will receive a virtual reality headset with one of three software programs:  
- Immersive Skills-Based VR therapy  
- Immersive Distraction VR therapy  
Non-immersive Sham VR Therapy with 2-D videos

**Study Duration:** 48 months

**Participant Duration:** 90 days

## 1.2 SCHEMA

### 1.3 SCHEDULE OF ACTIVITIES (SOA)

Procedures	Pre-screening	Screening Week Day -8 to -2	Enrollment Day -1 to 0	Day 1 (+ 6 days)	Day 7 (+ 6 days)	Day 15 (+ 6 days)	Day 21 (+ 6 days)	Day 30 (+ 6 days)	Day 45 (+ 6 days)	Day 60 (+ 6 days)	Day 75 (+ 6 days)	Day 90 (+ 6 days)
Prospective patient identified (DEEP 6 or provider registry)	X											
Confirm eligibility and Informed Consent via telephone and REDCap	X											
Online Pain Intensity Journal (7 days)		X										X
Screening Week Online Baseline Survey (see below)		X										
Randomization			X									
Participant receives study intervention kit			X									
Technical onboarding call				X								
Intervention: Participant uses VR therapy program and wears Fitbit Charge 4 watch				X	-----							X
Online survey: NIH HEAL Minimum Dataset	X											X
Immersive Tendency Questionnaire (ITQ)  and Motion Sickness Propensity Survey 	X											
Treatment expectation question	X											
Simulator Sickness Questionnaire (SSQ)  and Presence Survey				X								
Online survey: Primary outcome: PROMIS® Pain Interference	X			X	X	X	X	X	X	X	X	X
Discontinuation of Treatment Questionnaire				X	X	X	X	X	X	X	X	X
PROMIS® Physical Function  , Anxiety  , Depression  , Sleep disturbance  ; Pain intensity/interference with Enjoyment of life/interference with General activity (PEG)  , PCS-6 	X				X		X	X		X	X	X
EMR data: Charlson Comorbidity Index  , CURES and EMR: Prescription Data	X											X
Perceived study arm question, treatments in the last 90 days question												X
Online survey: PHQ-2, GAD-2, PGIC, TAPS [1/2]	X											X
Remote technical support				X	-----							X
End of study procedure question												X

Procedures	Pre-screening	Screening Week Day -8 to -2	Enrollment Day -1 to 0	Day 1 (+ 6 days)	Day 7 (+ 6 days)	Day 15 (+ 6 days)	Day 21 (+ 6 days)	Day 30 (+ 6 days)	Day 45 (+ 6 days)	Day 60 (+ 6 days)	Day 75 (+ 6 days)	Day 90 (+ 6 days)
Event Assessment: AE, SAE and UP review and reporting				X	X	X	X	X	X	X	X	X
ITQ: Immersive Tendency Questionnaire PEG: Pain, Enjoyment, General Activity PCS-SF: Pain Catastrophizing Scale-Short Form 6 PHQ-2: Patient Health Questionnaire-2 GAD-2: Generalized Anxiety Disorder 2-item PGIC: Patient Global Impression of Change TAPS: Tobacco, Alcohol, Prescription Medication, and Other Substance Use AE: Adverse event SAE: Serious adverse event UP: Unanticipated Problem												

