To assess the efficacy of Skills-Based and Distraction VR via patients' global impression of change (PGIC). The objective will be considered achieved if there is statistical evidence of higher rates of self-reported improvement in either VR group compared to control (sham) VR.	The overall effect of treatment from study baseline to Day 90 as measured by the PGIC is an exploratory endpoint. This scale measures self-reported belief regarding efficacy of treatment. A favorable response of 5-7 on the PGIC indicates significant improvement occurred over the course of the study. We will test for a statistically significant difference in PGIC responses between either VR group and control (sham) VR.	This exploratory endpoint will act as a check on internal validity for Primary and Secondary endpoints, and a general assessment of satisfaction with treatment.  The PGIC has established validity in measuring self-reported global change in cLBP trials. 
To assess the efficacy of Skills-Based and Distraction VR in improving wearable measures of physical activity from baseline to Day 90. The objective will be considered achieved if there is statistical evidence of measured improvement in either VR group compared to control (sham) VR.	The change from study baseline to Day 90 in weekly total steps as measured by FitBit is an exploratory endpoint. Change in steps will also be examined for interaction effects on the primary outcome.	There is evidence that physical activity can improve mood, sleep, and general health, yet persons with chronic pain may limit their activity because of their pain.  Evidence suggests that activity monitors encourage increased function and correlate with improvements in mood among patients with chronic pain. 

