To assess the efficacy of Skills-Based and Distraction VR in improving wearable measures of sleep from baseline to Day 90. The objective will be considered achieved if there is statistical evidence of measured improvement in either VR group compared to control (sham) VR.	The change from study baseline to Day 90 in sleep quantity (total minutes asleep as well as "sleep efficiency", see Section 4.6.3 for more info) as measured by FitBit is an exploratory endpoint. Changes in the seconds in sleep will also be examined for interaction effects on the primary outcome.	There is evidence that physical activity can improve mood, sleep, and general health, yet persons with chronic pain may limit their activity because of their pain.  Previous versions of the skills-based program used in this study showed improvements in the sleep subscale of a pain interference measure. 
Exploratory Subanalysis		
To assess subgroup analyses for the change from baseline in PROMIS-PI. An MMRM	The impact of the following variables mentioned in section	See Section 9.4.7 for details.

OBJECTIVES	ENDPOINTS	JUSTIFICATION FOR ENDPOINTS
model will be used to test for treatment by subgroup interactions.	9.4.7 will be assessed to changes in the primary outcome.	

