### 9.4 STATISTICAL ANALYSES

#### 9.4.1 GENERAL APPROACH

All statistical analyses will be performed jointly by the Cedars-Sinai Biostatistics Core and the Cedars-Sinai Center for Outcomes Research and Education (CS\_CORE) using SAS® software version 9.3 or higher (SAS Institute, Cary, NC, USA), R pack3.5.0 (R Foundation for Statistical Computing, Vienna, Austria) or Stata software version 14 or higher (StataCorp LLC, College Station, TX, USA).

Continuous variables will be summarized using descriptive statistics (N, mean, standard deviation, minimum, median, and maximum). Categorical variables will be summarized using the number and percentage of patients in each category. Data will be summarized with respect to patient demographic and baseline characteristics both across the study and by study-arm. The efficacy endpoints, safety assessments, and other outcome results for each treatment group will be summarized descriptively unless otherwise indicated. In addition, statistical model estimates of least squares means, treatment differences, p-values and 95% confidence intervals will also be provided where relevant. The fit of linear models will be assessed using residual plots and/or other diagnostic plots as appropriate. The fit of logistic models will be assessed using Hosmer-Lemeshow goodness-of-fit and/or receiver operating characteristic (ROC) curves as appropriate. All statistical tests will be 2-sided and performed at the 0.05 level of significance unless stated otherwise. Baseline is defined as the value at the screening week (Day -8 to Day -2) for all parameters, unless specified otherwise.

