## 4. STATISTICAL ANALYSES

### 4.1 General Methodology

All statistical analyses will be performed jointly by the Cedars-Sinai Biostatistics Core and the Cedars-Sinai Center for Outcomes Research and Education (CS\_CORE) using SAS® software version 9.3 or higher (SAS Institute, Cary, NC, USA), R pack 4.1.1 (R Foundation for Statistical Computing, Vienna, Austria) or Stata software version 14 or higher (StataCorp LLC, College Station, TX, USA).

Continuous variables will be summarized using descriptive statistics (N, mean, standard deviation, minimum, median, and maximum). Categorical variables will be summarized using the number and percentage of patients in each category. Data will be summarized with respect to patient demographic and baseline characteristics both across the study and by study-arm. The efficacy endpoints, safety assessments, and other outcome results for each treatment group will be summarized descriptively unless otherwise indicated. In addition, statistical model estimates of least squares means, treatment differences, p-values and 95% confidence intervals will also be provided where relevant. The fit of linear models will be assessed using residual plots and/or other diagnostic plots as appropriate. The fit of logistic models will be assessed using Hosmer-Lemeshow goodness-of-fit and/or receiver operating characteristic (ROC) curves as appropriate. All statistical tests will be 2-sided and performed at the 0.05 level of significance unless stated

otherwise. Baseline is defined as the value at the screening week for all parameters, unless specified otherwise.

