#### *Biometric Data – Steps*

We will assess the change from study baseline to Day 90 by comparing the treatment groups, separately, to the control group using a MMRM analysis. The repeated measures are the change from baseline weekly steps obtained for all weeks between Baseline and Day 90. The model will include fixed categorical effects for treatment, week, and the baseline weekly steps as a continuous covariate. We will employ the Stata xtmixed command or the R lmer function from the lme4 package with restricted maximum likelihood estimation (REML) and an unstructured within-patient covariance structure for this model. We will evaluate the assumptions of this model, including normality, using residual and other diagnostic plots of model fit.

From this model, we will estimate least squares means, standard errors, treatment differences in least squares means, and 95% confidence intervals for each time point. Primary inference will be based on the treatment comparison of least squares means at Day 90 from this model, and a p-value will be presented for this time point only. The null hypothesis is that the mean difference in the primary endpoint between the experimental arms and the sham arm is zero, versus the alternative hypothesis that this difference is not zero.

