#### *Biometric Data – Sleep*

We will assess the change from study baseline to Day 90 by comparing the treatment groups, separately, to the control group using a MMRM analysis. The repeated measures are the change from baseline weekly minutes classified as “sleep” obtained at weekly intervals between baseline and Day 90. The model will include fixed categorical effects for treatment, week, and baseline weekly steps as a continuous covariate. We will employ the Stata xtmixed command or the R lmer function from the lme4 package with restricted maximum likelihood estimation (REML) and an unstructured within-patient covariance structure for this model. We will evaluate the

assumptions of this model, including normality, using residual and other diagnostic plots of model fit.

From this model, we will estimate least squares means, standard errors, treatment differences in least squares means, and 95% confidence intervals for each time point. Primary inference will be based on the treatment comparison of least squares means at Day 90 from this model, and a p-value will be presented for this time point only. The null hypothesis is that the mean difference in the primary endpoint between the experimental arms and the sham arm is zero, versus the alternative hypothesis that this difference is not zero.

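### Fitbit steps and sleep are analysed as change from a screening-week baseline, but no Fitbit wear is scheduled before treatment and no other Fitbit baseline is defined

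*Protocol*

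**What the plan says.** **Endpoints.** Protocol section 3 lists two Fitbit endpoints, both tertiary/exploratory. For steps: "The change from study baseline to Day 90 in weekly total steps as measured by FitBit is an exploratory endpoint". For sleep, covering total minutes asleep and sleep efficiency: "The change from study baseline to Day 90 in sleep quantity". The wearable objectives in Protocol 1.1 and the steps endpoint in SAP 3.2 (Study Objectives and Endpoints) are also framed from baseline to Day 90.

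**Models.** In SAP 4.6.3 the steps model states: "The repeated measures are the change from baseline weekly steps obtained for all weeks between Baseline and Day 90". The sleep model states: "The repeated measures are the change from baseline weekly minutes classified as" sleep. Both models take baseline weekly steps as a continuous covariate.

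**Baseline.** Protocol 9.4.1: "Baseline is defined as the value at the screening week (Day -8 to Day -2) for all parameters, unless specified otherwise". SAP 4.1 agrees: "Baseline is defined as the value at the screening week for all parameters", with the same allowance for stated exceptions.

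**Device timing.** In the Schedule of Activities (Protocol 1.3), the row "Participant receives study intervention kit" is marked in the Enrollment column, Day -1 to 0, which also holds randomisation. The row "Intervention: Participant uses VR therapy program and wears Fitbit Charge 4 watch" starts on Day 1 and runs to Day 90. Protocol 1.1 makes the Fitbit a study device sent to the home along with the headset. Under Protocol 6.3 the headset ships with the assigned program already on it, so shipment follows randomisation.

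**The concern.** The baseline rule applies to every parameter that has no rule of its own, and the Fitbit measures have none. Applied literally, it asks for a weekly step count from a week in which the participant has not yet been sent the watch. Both the response (change from baseline) and the covariate (baseline weekly steps) fail for that reason.

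The analyst would have to improvise. The nearest available substitute is the first week of wear, which comes after randomisation and during use of the assigned program. If the program already affects steps or sleep in that week, subtracting and adjusting for the week-1 value removes part of the effect being estimated. Choosing a substitute after seeing the data would also be a data-dependent decision.

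Three other uses of the data share the gap: sleep efficiency, the planned look at change in steps and sleep for interaction with the primary outcome (Protocol section 3), and any Fitbit activity measure tabulated at baseline (Protocol 9.4.5, SAP 4.4).

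**Working it through.** **Step 1. Overlap of baseline window and wear.** The plan gives no figure to reproduce here; the check is a count of days.

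- Baseline window (Protocol 9.4.1): Day -8 to Day -2, which is 7 days.
- Scheduled Fitbit wear (Protocol 1.3): Day 1 to Day 90.
- Days in common: 0.
- If the watch were worn from kit receipt, Day -1 and Day 0 would add at most 2 scheduled days before VR use. Neither lies in the window, both are in the enrolment and randomisation column, and 2 days do not make a weekly total.

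**Step 2. Search for an exception.** Both baseline rules allow one. The places where it could stand are Protocol 8.2.1 (Fitbit data), 9.4.5, 9.4.9 and 10.1.9.1, and SAP 4.4 and 4.6.3. None defines a Fitbit baseline or a run-in. Protocol 5.4 describes the screening week as a daily pain question plus baseline surveys, before randomisation. SAP 5.2, reserved for changes to planned analyses, is still a placeholder.

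**Step 3. Consequence of using week 1 of wear.** This is conditional, because the plan does not name week 1. Let D90 be the true between-arm difference at Day 90, D1 the difference already present in week 1, f = D1/D90, and beta the within-arm slope of the Day 90 value on the week-1 value. With week 1 as covariate, the arm means satisfy

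D90 = tau + beta × D1, so tau = D90 × (1 - beta × f),

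where tau is the estimated arm effect. Taking change from week 1 as the response shifts the slope to beta - 1 and leaves tau the same. The documents give neither f nor beta, so both are varied as assumptions:

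| f | beta 0.5 | beta 0.7 | beta 0.9 |
|---|---|---|---|
| 0 | 1.00 | 1.00 | 1.00 |
| 0.25 | 0.875 | 0.825 | 0.775 |
| 0.5 | 0.75 | 0.65 | 0.55 |
| 0.75 | 0.625 | 0.475 | 0.325 |
| 1 | 0.50 | 0.30 | 0.10 |

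Entries are the share of the Day 90 effect retained. For example, f = 0.5 and beta = 0.7 gives 1 - 0.7 × 0.5 = 0.65. A simulation at those values, regressing change on arm and week-1 value, returned 0.652.

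**Step 4. The alternative.** A direct between-arm comparison of post-randomisation values uses no Fitbit baseline, so this attenuation does not arise.

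**The case against.** Three objections have force.

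*A plan cannot show what data exist.* A reader might infer that no pre-treatment Fitbit value exists for anyone. The documents do not support that. Devices travel by courier, and Protocol 7.3 allows up to 30 days after delivery to schedule the onboarding call, so some participants may have worn the watch before first using VR. Such wear would be unrequested, undefined as baseline, after randomisation and outside Day -8 to -2. It does not supply the missing baseline, but the supportable statement is that none is planned or defined.

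*The bias belongs to an analysis the plan never names.* This stands. A reader might also take the bottom row of the table as the expected loss. That row needs the full Day 90 effect to be present in week 1, which is doubtful as the only scenario for a Skills-Based arm built on a 56-day sequenced program (Protocol 4.3, 6.1.1). The direction, toward no effect, also needs a week-1 effect of the same sign.

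*The endpoints are exploratory.* This stands too. A reader might infer a threat to the main result, because physical activity is in the title and Protocol 4.1 includes biometric outcomes in the stated primary hypothesis. But trial success (Protocol section 3, 9.4.2) and sample size (9.2) rest on PROMIS Pain Interference alone, and SAP 6.3 puts exploratory tests outside the gatekeeping.

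None of these makes the change score or the covariate computable.

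**Conclusion.** The point holds as a contradiction between the baseline rule, the device schedule and the Fitbit models: 0 of 7 baseline days have scheduled wear, and no exception is stated. That conclusion rests on the documents alone.

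The size of any bias is conditional. It arises only if on-treatment week 1 is made the baseline. For beta between 0.5 and 0.9, about 78-88% of the Day 90 effect would be kept at f = 0.25, 55-75% at f = 0.5 and 10-50% at f = 1, with no bias at f = 0. Both f and beta are assumptions.

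The reach is limited to the exploratory Fitbit endpoints, the interaction analyses that use change in steps or sleep, and any Fitbit values tabulated at baseline. The primary PROMIS Pain Interference analysis and the sample size do not change. It should be corrected before analysis, but it does not endanger the trial's main conclusion.

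**What to change.** - **Endpoints.** In Protocol 1.1 and section 3, and in SAP 3.2 and 4.6.3 (Biometric Data – Steps and – Sleep), replace change from baseline with post-randomisation weekly steps, weekly sleep minutes and sleep efficiency, compared directly between arms. Protocol 9.4.9 describes these outcomes only as over time, so it has no change-from-baseline wording to remove.
- **Covariates.** Remove baseline weekly steps from both models. Adjust instead for pre-randomisation PROMIS Physical Function in the steps model and PROMIS Sleep Disturbance in the sleep model; both are already collected.
- **Week 1.** State that the first on-treatment week of wear will not serve as baseline.
- **Interaction analyses.** Restate those that use change in steps or sleep so that they need no Fitbit baseline.

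The cost is wording in the two documents, with no new data collection. The downside is less precision than a true Fitbit baseline would have given.

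There are two alternatives. A labelled post-randomisation Fitbit baseline would be computable but carries the bias shown above. A pre-randomisation run-in would supply a real baseline, but by the plan's own dates (randomisation to 5 September 2023 in Protocol 8.1, this version dated 19 October 2023) it appears to be too late.
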